4.2 Toxities and Dosing Delays/Dose Modifications

Any patient who receives treatment on this protocol will be evaluable for toxicity. Each patient will be assessed for the development of toxicity according to the Time and Events table. Toxicity will be assessed according to the NCI Common Toxicity Criteria for Adverse Events (CTCAE), version 4.0. Dose adjustments should be made according to the system showing the greatest degree of toxicity.

N/A

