4.7 Removal of Patients from Protocol Therapy

Patients will be removed from therapy when any of the criteria listed in Section 5.5 apply. Notify the Principal Investigator, and document the reason for study removal and the date the patient was removed in the Case Report Form. The patient should be followed-up per protocol.

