4.8 Patient Replacement

If any patient expires, is converted to open surgery, or requires a return to the operating room they will be removed from the study.

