10.3 Data Analyses Plans

Analysis of Co-Primary Endpoints:

The distribution of VAS pain scores in each group will be examined and assessed for normality and homoscedasticity, visually, by generating probability-probability (P-P) plots, boxplots, stem-and-leaf plots and quantile-quantile (Q-Q) plots, and with the Shapiro-Wilk normality test. If necessary, a transformation of the data will be made to render appropriate for parametric testing. All analyses will be performed on patients who undergo surgery and have a 24 hour VAS pain score assessment. Balance on baseline characteristics (including gender, age at surgery, height, weight, BMI, and operative time) among the randomized groups will be assessed separately for each intervention, using the standardized difference. Any variable with an absolute standardized difference >0.52 (i.e., $1.96 \times 1/n_1 + 1/n_2$) for either intervention will be adjusted for in secondary analyses.^{13,14}

A step-down hierarchical hypothesis testing approach will be used to test the two hypotheses (co-primary endpoints). In the first step, to establish assay sensitivity, the alternative hypothesis that the 24-hour post-operative mean VAS pain score in the UTAP group is superior to that in the placebo group will be tested by a one-sided two sample t-test at the 0.025 level of significance ($H_{01}: \mu_{UTAP} \geq \mu_{Placebo}$ vs. $H_{A1}: \mu_{UTAP} < \mu_{Placebo}$).

If assay sensitivity is demonstrated in the first step by rejecting the null hypothesis, H_{01} , we will proceed to the second step of testing for non-inferiority of LTAP to UTAP. To establish non-inferiority, the alternative hypothesis that LTAP is non-inferior to UTAP will be tested using the ‘fractional approach’ introduced by Pigeot et al (2003) where the effect estimate is based on the ratio of the differences in means between LTAP and placebo and UTAP and placebo ($H_{02}: \frac{\mu_{LTAP} - \mu_{Placebo}}{\mu_{UTAP} - \mu_{Placebo}} \leq \theta$: vs. $H_{A2}: \frac{\mu_{LTAP} - \mu_{Placebo}}{\mu_{UTAP} - \mu_{Placebo}} > \theta$).

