The secondary endpoints, including length of hospital stay and days to return of bowel function will be analyzed depending on existence of event censoring and/or occurrence of competing events at the time of analysis. Length of hospital stay will be calculated as the number of days between the date of surgery and the date of discharge from the hospital. Days to return of bowel function will be calculated as the number of days between the date of surgery and the date of first bowel movement. If the event is observed in all patients and there is no censoring at the time of analysis, the mean and standard deviation (if normally distributed) or median and IQR (if skewed) will be presented and an analysis of variance (or Kruskal-Wallis analysis of variance) will be used to compare means (or distributions) among groups, respectively. If the event is not observed in all patients (censoring at time of analysis) then the method of Kaplan-Meier will be used to estimate the median times to event and corresponding 95% confidence intervals will be constructed based on the method of Brookmeyer and Crowley.¹⁸ Comparisons of time to event distributions among intervention groups will be made with the log-rank test. If competing events are observed, such as death prior to the event of interest, then cumulative incidence functions (CIF) will be estimated in a competing risk setting. In these analyses, discharge and first bowel movement will be the defining events in each analysis while death without discharge or prior bowel movement will be considered the competing event. Patients who are alive and have not yet been discharged or have not had return of bowel function as of the data analysis cutoff will be censored. CIF comparisons among intervention groups will be made with Gray's test.¹⁹

The secondary endpoint of procedure related complications including bleeding or injection of anesthetic intravascular will be determined according to Common Terminology Criteria for Adverse Events (CTCAE v 4.0) and presented as frequency at each grade. A Poisson regression model will be used to test the difference in adverse event rates between the two groups. In this model, the numerator is the number of adverse events and the denominator (offset) is the natural log of the person days followed.

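### Read literally, section 10.3 confines the complication endpoint to patients with a 24-hour VAS, in conflict with section 4.2, and section 4.8 leaves the events of removed patients unassigned

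*Combined protocol and SAP*

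**What the plan says.** Section 10.3 gives one analysis population: "All analyses will be performed on patients who undergo surgery and have a 24 hour VAS pain score assessment". It appears under the heading "Analysis of Co-Primary Endpoints", after the checks on the distribution of the VAS scores and before the check of baseline balance.

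Later in 10.3, among the secondary endpoints, the safety analysis reads: "The secondary endpoint of procedure related complications including bleeding or injection of anesthetic intravascular will be determined according to Common Terminology Criteria for Adverse Events". It is to be shown as frequencies by grade and compared by Poisson regression, in which "the denominator (offset) is the natural log of the person days followed". No population is named there, and no safety set is defined anywhere in the statistical section.

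Three clauses in the treatment plan bear on the same patients:

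- Section 4.2: "Any patient who receives treatment on this protocol will be evaluable for toxicity".
- Section 4.8: "If any patient expires, is converted to open surgery, or requires a return to the operating room they will be removed from the study".
- Section 4.7, on patients taken off therapy under the section 5.5 criteria: "The patient should be followed-up per protocol".

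**The concern.** Under section 6.1.1 the VAS is a mark that the patient makes by hand. Having a 24-hour score is therefore a post-treatment condition, and an early serious complication can prevent it: a patient who is sedated, ventilated, back in theatre or dead at 24 hours makes no mark. If that condition governs the complication analysis, the event being counted can remove the patient from the count. Section 4.8 can do the same without reference to the VAS. Return to the operating room is a foreseeable result of bleeding, which the endpoint names.

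What is at stake is the final complication table and the comparison between arms. Sections 1.1 and 6.5 say that the cited trials reported no complications with the injections, so few events are expected and each carries weight. Section 1.1 also says that no published data compare the laparoscopic with the ultrasound-guided block, so this trial's comparative complication data would be informative. If early serious events differ between guidance methods, the loss could also differ between arms.

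**Working it through.** The plan states no figure that depends on this population, so there is nothing to reproduce. The check is a reading of the clauses together, followed by an illustration.

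**Reading the clauses**

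1. *Wide reading of 10.3.* The sentence refers to all analyses, and complications are a secondary endpoint (section 2.4). The same paragraph also covers baseline balance and adjustment in secondary analyses, so it works partly as a general preamble. On this reading the complication analysis needs a 24-hour VAS, and 10.3 conflicts with 4.2.
2. *Narrow reading of 10.3.* The heading limits the sentence to the co-primary pain analyses. There is then no conflict with 4.2, but the analysis plan states no safety population.
3. *Section 4.8 on either reading.* Patients who die, are converted to open surgery or return to the operating room leave the study. The plan does not say whether their events stay in the analysis. The follow-up clause in 4.7 concerns removal from therapy under 5.5, so it does not settle this.
4. *What is collected.* The Time and Events Table (section 5.4) schedules adverse event monitoring at 4–6, 12 and 24 hours and at the follow-up visit, with no link to having a VAS. The data for an all-treated analysis are therefore already planned.

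**Illustration**

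Inputs: 94 patients in each TAP arm, so 188 in both (section 10.2). The documents give neither a complication rate nor a rate of missing 24-hour VAS, so the following are assumptions: *k* patients have a complication, *m* of them are excluded, and nobody else is excluded.

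- Rate in all treated patients = *k*/*n*
- Rate in the restricted set = (*k* − *m*)/(*n* − *m*)

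| *n* | *k* | *m* | All treated | Restricted set |
|---|---|---|---|---|
| 94 | 1 | 1 | 1/94 = 1.06% | 0/93 = 0% |
| 94 | 2 | 0 | 2/94 = 2.13% | 2/94 = 2.13% |
| 94 | 2 | 1 | 2/94 = 2.13% | 1/93 = 1.08% |
| 188 | 2 | 1 | 2/188 = 1.06% | 1/187 = 0.53% |
| 188 | 2 | 2 | 2/188 = 1.06% | 0/186 = 0% |

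In general, with true rate *p* and a fraction *f* of affected patients excluded, the restricted set estimates *p*(1 − *f*)/(1 − *pf*). For *p* = 2% this gives:

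- *f* = 0: 2.00%
- *f* = 0.25: 0.02 × 0.75/0.995 = 1.51%
- *f* = 0.5: 0.02 × 0.5/0.99 = 1.01%
- *f* = 1: 0%

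For rare events the reported rate thus falls roughly in proportion to *f*. The person-days offset does not correct this, because an excluded patient takes the event and the follow-up time out together. If affected and unaffected patients were excluded equally often, the expected bias in these proportions would vanish. The problem arises only when exclusion is related to the complication.

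**The case against.** The strongest reply is the placement of the sentence. It sits under the co-primary heading among steps that concern the VAS, the secondary endpoints have a heading of their own, and the restriction is not repeated there. Section 4.2 gives a specific rule for toxicity, which can be read as governing safety. This stands as a possible reading, so a flat contradiction between 10.3 and 4.2 is not proved. It does not remove the point: on the narrow reading 10.3 still has no safety population and 4.8 is still unresolved, so the same correction is needed.

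Three stronger readings are tempting, and the documents do not support them.

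- *A reader might infer that the most harmed patients will drop out of the analysis.* The documents show only that they can. A patient with bleeding or an intravascular injection may still give a score at 24 hours, and no rate of missing scores is given.
- *A reader might infer that lost events would change a verdict against the 5% level.* That level is in section 6.5 on stopping. Section 10.3 plans grade frequencies and a Poisson model, with no confidence interval set against 5%.
- *A reader might infer that patient safety oversight is weakened.* Adverse event collection (5.4), expedited reporting (6.3.5.1) and the section 6.5 trigger, under which one serious TAP-related complication halts accrual and calls for a DSMB meeting, do not use the 10.3 set. For the same reason, an illustration with one lost event is more realistic than one with several serious events.

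**Conclusion.** The point holds as a conflict between clauses on the literal reading and as an undefined safety population on the narrow one. Either way, patients with early serious complications can be lost from the final complication frequencies and the between-arm Poisson comparison, through the VAS condition or through section 4.8.

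The size cannot be determined from the documents. It is zero if every affected patient has a 24-hour VAS and stays in the study. If one affected patient in a TAP arm is excluded and there are no other events, the arm reports 0/93 in place of 1/94. That example rests on assumed counts and on nobody else being excluded. Neither co-primary hypothesis depends on how the safety set is defined. Severity: should-fix.

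**What to change.** Make three changes before any analysis by arm, since a safety denominator chosen once events are known would be open to challenge.

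1. In 10.3, limit the requirement for a 24-hour VAS to the 24-hour pain analyses.
2. In 10.3, add a safety set, for example: *Safety analyses include every patient who received a study injection (UTAP, LTAP or local infiltration), whether or not a 24-hour VAS was recorded. Adverse events and person-days of patients removed under section 4.8 are included up to the end of their follow-up.*
3. Reconcile 4.2, 4.8 and 10.3, so that 4.8 says how removal from the study affects the safety data already collected and any follow-up still due.

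The cost is a few sentences. No patients or visits are added, because adverse event monitoring is already scheduled without regard to the VAS. The reported complication rate may be slightly less favourable.

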1.4 Rationale

We aim to prospectively compare Placebo (local administration), UTAP, and LTAP blocks in patients undergoing surgery of the prostate and kidney. We expect to be able to equally efficiently administer the blocks using direct visualization and ultrasound guidance. We expect that a negative result would obviate the need for longer operative time by eliminating the need for the separate ultrasound guided block while a positive result would demonstrate the increased utility of preoperative ultrasound blocks in managing postoperative pain.

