4.0 TREATMENT PLAN**4.1 Treatment Dosage and Administration**

- 4.1.1 30mL of 0.25% bupivacaine will be administered to bilateral TAP using ultrasound or laparoscopic guidance in prostatectomies. 40ml 0.25%

bupivacaine unilateral will be administered in nephrectomy patients (weight based dosage permitting). Placebo groups will receive direct injection of bupivacaine into surgical wounds.

4.1.2 The anesthesia protocol will be at the discretion of the anesthesiologist, including premedication, induction of anesthesia, endotracheal intubation, and maintenance of sedation and neuromuscular blockade. Similarly, all patients will undergo standardized procedure for obtaining pneumoperitoneum and insertion of laparoscopic ports.

Patients in the UTAP group will receive abdominal wall nerve block by the anesthesia team with 30 cc of 0.25% Bupivacaine in bilateral TAP regions under ultrasound guidance (percutaneously) after obtaining general anesthesia. (unilateral 40ml for nephrectomies) Conversely, patients in the LTAP group will undergo bilateral nerve blocks by the surgical team under direct vision from an intraabdominal access after creating pneumoperitoneum and inserting the laparoscope. Patients in the Placebo will receive injection of bupivacaine directly into the surgical wound.

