5.0 STUDY PROCEDURES**5.1 Screening/Baseline Procedures**

Assessments performed exclusively to determine eligibility for this study will be done only after obtaining informed consent. Assessments performed for clinical indications (not exclusively to determine study eligibility) may be used for baseline values even if the studies were done before informed consent was obtained.

All screening procedures must be performed within 0 days prior to registration unless otherwise stated. The screening procedures include:

5.1.1 *Informed Consent***5.1.2 *Medical history***

Complete medical and surgical history, history of infections

5.1.3 *Demographics*

Age, gender, race, ethnicity

5.1.4 *Review subject eligibility criteria***5.1.5 *Review previous and concomitant medications*****5.1.6 *Physical exam including vital signs, height and weight***

Vital signs (temperature, pulse, respirations, blood pressure), height, weight

5.1.7 *Adverse event assessment*

Baseline adverse events will be assessed. See section 6 for Adverse Event monitoring and reporting.

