10.0 STATISTICAL CONSIDERATIONS**10.1 Study Design/Study Endpoints**

This is a single-center, single-blinded, (stratified) randomized placebo-controlled three-arm non-inferiority trial with 2:2:1 allocation ratio.

Randomization:

People who meet eligibility requirements and provide informed consent will be randomly allocated to 3 groups to receive either UTAP, LTAP or Placebo with a 2:2:1 allocation ratio. The allocation sequence will be stratified by type of surgery (prostatectomy or partial nephrectomy) using stratified block randomization with randomly varying block sizes. Random permuted blocks sizes within stratification groups will be used to minimize the chance of selection bias. Investigators will be blinded to the size of each block with only the study statistician responsible for generating the randomization list knowing this information. A randomization service called Sealedenvelope.com available at <https://www.sealedenvelope.com/simple-randomiser/v1/> will be used for allocation concealment to ensure that retrieval of the treatment group assignment is only revealed to appropriate team members on a real time basis after each new patient has been screened and consented. This service allows for allocation concealment that would not be possible if the entire randomization list was made available to team members at the beginning of the study. The security and integrity of the codes used by Sealedenvelope.com follows the Food and Drug Administration (FDA) standards for electronic records and follows the International Conference on Harmonisation Good Clinical Practice (ICH GCP) guidelines.

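### Operative time is measured after randomisation, yet section 10.3 lists it as a baseline characteristic that can trigger covariate adjustment

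*Combined protocol and SAP*

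**What the plan says.** All references are to the combined protocol and SAP.

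- **The rule (section 10.3, under the co-primary endpoints).** "Balance on baseline characteristics (including gender, age at surgery, height, weight, BMI, and operative time) among the randomized groups" is to be assessed by the standardised difference, separately for each intervention. "Any variable with an absolute standardized difference >0.52", a value that the plan equates with a formula in n1 and n2, "for either intervention will be adjusted for in secondary analyses". The secondary analyses are not named.
- **Allocation (section 10.1).** "People who meet eligibility requirements and provide informed consent will be randomly allocated to 3 groups". Assignment is revealed once a patient has been screened and has consented. "The allocation sequence will be stratified by type of surgery (prostatectomy or partial nephrectomy").
- **Delivery of the blocks (section 4.1).** The anaesthesia team gives the ultrasound-guided block once general anaesthesia is established. The laparoscopic block is given "by the surgical team under direct vision from an intraabdominal access after creating pneumoperitoneum and inserting the laparoscope".
- **Expected effect on time (section 1.4).** The rationale says that "a negative result would obviate the need for longer operative time by eliminating the need for the separate ultrasound guided block".
- **Baseline data (section 5.1).** The physical measurements collected at screening are "Vital signs (temperature, pulse, respirations, blood pressure), height, weight". Operative time is not among the screening items.
- **Outcomes (sections 2.4 and 10.3).** Operating room time and surgical time are secondary endpoints, compared across the three arms.

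**The concern.** A balance check on baseline variables looks for chance differences that were present before treatment. Adjusting for such a variable leaves the target of the comparison unchanged. A variable that arises after allocation and can respond to it is different: a difference between arms may be part of what the treatment did.

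Operative time is of that second kind, and the rule then works the wrong way round. The more a block changes operative time, the more likely the variable is to pass the threshold and be adjusted for. If the length of the operation affects the outcome, adjustment removes that part of the block effect. If surgical difficulty drives both operative time and the outcome, adjustment can create an association between block and difficulty that randomisation had excluded. What is at stake is the interpretation of whichever adjusted secondary comparisons are reported.

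A second, smaller matter is that 0.52 does not obviously follow from the formula given for it.

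**Working it through.** **1. Is operative time a baseline variable?** Four places in the plan bear on this.

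- Timing: section 10.1 allocates after screening and consent, and operative time is known only after surgery.
- Mechanism: under section 4.1 the laparoscopic block is given inside the operation, whereas the ultrasound block is a separate step by another team.
- The plan's expectation: section 1.4 ties the separate ultrasound block to longer operative time.
- Status: section 5.1 does not collect it at baseline, and sections 2.4 and 10.3 treat closely related times as outcomes.

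All four point the same way. No arithmetic is needed for this conclusion.

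**2. Where could the adjustment enter?** The sentence stands under the co-primary heading, so it may mean a supportive adjusted analysis of VAS pain. Among the secondary-endpoint methods, the log-binomial model (antiemetic use), the Poisson model (adverse events) and the analysis of variance (length of stay, return of bowel function) could all take covariates. The one-sided t-test and the Fieller bound are specified without any.

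**3. The 0.52 threshold.** The inputs are z = 1.96 and 0.52 from section 10.3, and arms of 94, 94 and 47 from section 10.2. The formula as it appears in the text has no root sign, which may be a loss in PDF extraction. Taken literally and bracketed, it gives 1.96 × (1/94 + 1/47) = 0.063, so it does not yield 0.52. With the root restored, the threshold is 1.96 × sqrt(1/n1 + 1/n2):

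| Reading of intervention | n1 v n2 | Threshold |
|---|---|---|
| Block arm, block v placebo | 94 v 47 | 1.96 × 0.1786 = 0.350 |
| Block arm, LTAP v UTAP | 94 v 94 | 1.96 × 0.1459 = 0.286 |
| Surgery type, even split, block v placebo | 47 v 23.5 | 0.495 |
| Surgery type, even split, LTAP v UTAP | 47 v 47 | 0.404 |

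The plan's figure can also be inverted. In a stratum of N patients allocated 2:2:1, block v placebo has 1/n1 + 1/n2 = 2.5/N + 5/N = 7.5/N. So 0.52 needs N = 7.5 × (1.96/0.52)² = 106.6. Two equal strata of that size make about 213 analysed patients, a loss of 22/235, or about 9%. The plan states neither a split nor a loss rate, so this can be neither confirmed nor excluded.

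**4. What the threshold changes for true baseline variables.** At 94 v 47, 0.52 corresponds to z = 0.52/0.1786 = 2.91. A variable balanced in expectation then exceeds it with probability 0.36%, against 5% at 0.350. On the surgery-type reading with an even split, the figure is 4.0% against 5%.

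**5. How the two points interact (illustration only).** Assume a true difference d in operative time between a block arm and placebo of 0.1, 0.3 or 0.5 SD; the documents give no value. With SE = 0.1786, the chance of being flagged is 1 − Φ((t − d)/SE) + Φ((−t − d)/SE):

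| d | t = 0.52 | t = 0.350 |
|---|---|---|
| 0.1 | 1.0% | 8.7% |
| 0.3 | 10.9% | 39.0% |
| 0.5 | 45.5% | 79.9% |

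Lowering the threshold while operative time stays in the list makes the main problem more likely to occur.

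**The case against.** The strongest reply has four parts.

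- **The harm is not demonstrated.** Distortion needs a path from block-driven minutes to the outcome, or a shared cause, and the documents give no data on either. Section 1.4 also expects the two blocks to be given equally efficiently. Operative time is undefined, and section 4.1 does not say that the ultrasound block falls within surgical time. This stands as a limit on size: the bias may be small or nil. It does not make the variable a baseline one, because operative time is measured after allocation on any definition.
- **The list looks prognostic.** The sentence cites a paper whose title concerns predictors of postoperative pain and analgesic use. That may explain the inclusion but does not cure the timing. If operative time does predict pain, conditioning on it has more effect, not less.
- **Only secondary analyses are touched.** This stands in full.
- **The threshold may be right.** Balance among the randomised groups, assessed separately for each intervention, is hard to parse if intervention means arm, and *either* fits the two surgery types. Against that, section 10.3 also calls the three arms intervention groups. Section 10.3 restricts the analysis to operated patients with a 24-hour score and section 4.8 removes some patients, so an analysed n below 235 is foreseen. The wording is ambiguous, and this part of the reply largely stands.

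**Conclusion.** Operative time is wrongly classed as a baseline characteristic. This rests only on the order of events and on the plan's own statement that the block can affect operative time. The consequence is confined to adjusted secondary analyses, including a supportive adjusted VAS analysis if that is what is meant. The size cannot be computed from the documents, and the flagging probabilities above depend on assumed differences.

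Two stronger readings are tempting and are not supported:

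- A reader might infer that the non-inferiority conclusion itself is at risk. It is not: both co-primary tests are unadjusted, and the sample size does not depend on this rule.
- A reader might infer that 0.52 is a miscalculation, or is left over from a smaller design. The figure is not reproduced at the planned arm sizes (0.35 and 0.29). That comparison assumes a restored root sign and takes intervention to mean block arm. On the surgery-type reading the formula comes close, at about 0.50 for block v placebo. Nothing in the documents speaks of an earlier design.

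Even on the arm reading, the chance imbalances that go unflagged do not bias the unadjusted randomised comparison. The threshold point is therefore minor and conditional.

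**What to change.** 1. Delete operative time from the balance check and from the adjustment set in section 10.3. Report it, if at all, with operating room time and surgical time, and define how it differs from them.
2. State whether intervention means block arm or type of surgery, and which pairs of groups are compared. Replace the fixed 0.52 with 1.96 × sqrt(1/n1 + 1/n2), root sign shown, evaluated at the n of each comparison actually made. Make this change only together with the first.
3. Name the secondary analyses in which flagged variables are adjusted for, and say whether an adjusted analysis of 24-hour VAS pain is one of them.

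The cost is a wording change to the analysis plan. No new data are needed, and the co-primary analysis and the sample size stay as they are. It is best made before outcome data are seen, because dropping operative time after an imbalance appears would look data-driven.
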